**VII.B.1.b** **Provide the [NCT](#) (National ClinicalTrials.gov Identifier) number**  
NCT03619135

**VII.B.2** **Does this project involve a [drug washout](#) (asking subject to stop taking any drugs s/he is currently taking)?**  
No

**VII.B.6** **Will any subjects receive a [placebo](#) in this study when, if they were not participating, they could be receiving an FDA-approved treatment for their condition?**  
No

**VII.B.11** **Is there a separate, written protocol that will be submitted in addition to this IRB New Project form? (Note: a grant application is not considered to be a protocol)**  
No

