**VII.E.1.a**      **Will any subjects be blinded to which study arm they have been assigned?**  
No

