**VII.E.2**      **Describe randomization scheme/assignment including ratio such as 1:1, 2:1 etc.**  
The study will be made of two randomized groups with a 1:1 ratio. Those who use the Buzzy system (experimental group) and normal, routine IV start without Buzzy (control).

An equal number of forms noting Buzzy (experimental) and Standard (control) will be printed and placed in security envelopes. These will be randomly mixed and when an eligible and participating subject is identified, the top most envelope will be chosen and opened to assign the group.

**VII.E.3**      **Will any questionnaires, surveys, or written assessments be used to obtain data directly from subjects in this study?**  
Yes

**VII.E.4**      **List all questionnaires, surveys, written assessments and ATTACH each one to the application. (NOTE: You are NOT prohibited from attaching copyrighted materials to this application)**  
A single questionnaire with before and after placement of intravenous catheter

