### DESCRIBE:

- **What subjects will be asked to do/what happens in the study (in sequential order)**
- **The time period over which procedures will occur**
- **The time commitment for the subject for individual visits/procedures**
- **Long-term followup and how it occurs**

The participants will be randomized into two groups, those who use the Buzzy system (experimental), and routine IV start (control). Prior to knowing their group, all patients will answer the "Before Intravenous Catheterization" portion of the form in order to eliminate bias. After this portion is complete, their group (experimental vs control) will be determined from opening a blinded envelope.

A tourniquet will be placed, followed by the Buzzy stimulation device (if in the experimental group). An alcohol swab will be used and then a 22 gauge IV catheter will be inserted, connected to fluids, and secured with tape. The antecubital fossa or the dorsal hand/wrist will be the only sites used in the study. All participants will fill out the post-insertion questions on the form and those patients that used the Buzzy system will then fill out the several specific questions related to the experimental group. This will conclude the patient's involvement in the study. The patient will then continue with treatment as planned. We will plan to exclude cases where the IV is not obtained on the first attempt, if a smaller or larger gauge IV catheter is required, or if an insertion site not listed above is required. The case will be excluded if adjunctive steps are taken to obtain IV access (i.e. Oral sedation, nitrous oxide, heat packs).

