## XI. Data Analysis

**XI.1** **Describe the analysis methods you will use, including, if applicable, the variables you will analyze**  
Simple descriptive statistics would be used to summarize the data. Normality of data will be assessed by Kolmogirov Smirnov test. Continuous outcomes would be assessed by t-tests, ANOVA, and multivariable linear regression models. Categorical variables would be assessed by Chi-square tests and multivariable logistic regression models. All tests will be two sided and a p-value of <0.05 would be set for statistical significance.

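### Randomised patients whose first IV attempt fails are excluded and no all-randomised analysis is planned, so the pain comparison is not protected by randomisation and may be biased in either direction

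*Combined protocol and SAP*

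**What the plan says.** Section VII.E.6 fixes the order of events. Patients answer the baseline questions; then "After this portion is complete, their group (experimental vs control) will be determined from opening a blinded envelope". The tourniquet follows, then the device in the experimental arm only, then the needle. The section goes on: "We will plan to exclude cases where the IV is not obtained on the first attempt". It also excludes cases needing another catheter gauge, an unlisted site or adjunctive steps.

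Section XI.2 confirms that missed attempts are expected to be excluded: it gives them as one reason for enrolling up to 100 patients when 76 are required.

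Section XI.1 lists methods ("Continuous outcomes would be assessed by t-tests, ANOVA, and multivariable linear regression models") but names no analysis population, no analysis of all randomised patients and no reporting of exclusions by arm. Section VII.B.11 answers No to "Is there a separate, written protocol that will be submitted in addition to this IRB New Project form", so no other submitted protocol fills the gap. Section VII.E.1.a answers No to "Will any subjects be blinded to which study arm they have been assigned".

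Two statements bear on whether ratings after a failed attempt exist. Section VII.E.6 says "All participants will fill out the post-insertion questions on the form", which suggests they do. Section VII.E.4 describes the form as "A single questionnaire with before and after placement of intravenous catheter", which leaves room for the rating to be skipped after a miss, or to refer to a later attempt.

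**The concern.** Randomisation makes the two arms comparable at the moment the envelope is opened. First-attempt failure comes later and, in one arm, with the device in place next to the insertion site. The documents neither show nor rule out that the device changes the chance of success. If it does, or if different kinds of patient fail in the two arms, dropping the failures leaves groups that differ for reasons other than the effect of the device on pain. The difference could then flatter the device or count against it.

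A second problem remains even without that bias. Section I.5 asks about pain during cannulation in adults, not about pain during insertions that succeed first time. An analysis restricted to successes answers the narrower question without saying so.

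The gauge, site and adjunct exclusions are less clear-cut. Section VII.E.2 says that "when an eligible and participating subject is identified, the top most envelope will be chosen and opened to assign the group", which is compatible with judging those needs before allocation. For them the plan only has to say when the decision is made.

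**Working it through.** **Inputs from the plan (XI.1, XI.2, VII.E.2).** SD 3.10, difference 2 points, two-sided alpha 0.05, power 80%, 1:1 allocation, 38 per arm (76 in total), enrolment up to 100.

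**The plan's own figure.** n per arm = 2 × [3.10 × (1.960 + 0.842) / 2]² = 37.71, rounded up to 38. This reproduces. The 100 − 76 = 24 extra places are room for exclusions, not a forecast of them.

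**Assumed, because the documents are silent.** Failure rates by arm (fB for Buzzy, fC for control) and the excess D, the mean pain of excluded minus retained patients.

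**A. No true difference between the full arms; failing patients would score higher anyway.** Each retained mean is the full-arm mean minus f × D, so

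bias (Buzzy − control) = −(fB − fC) × D.

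Type I error follows from bias / SE, with SE = 3.10 × √[1/(50(1 − fB)) + 1/(50(1 − fC))]. For 34% versus 14% and D = 3: bias = −0.20 × 3 = −0.60; SE = 3.10 × √(1/33 + 1/43) = 0.717; ratio 0.836; two-sided rejection about 13%.

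| Failures, Buzzy / control | D | Bias (negative favours Buzzy) | Type I error |
|---|---|---|---|
| 24% / 24% | 3 | 0 | 5% |
| 6% / 4% | 3 | −0.06 | about 5% |
| 10% / 5% | 2 | −0.10 | about 5% |
| 29% / 19% | 1 | −0.10 | about 5% |
| 34% / 14% | 1 | −0.20 | about 6% |
| 15% / 5% | 3 | −0.30 | about 7% |
| 29% / 19% | 3 | −0.30 | about 7% |
| 34% / 14% | 3 | −0.60 | about 13% |

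Swapping the arms reverses the sign and leaves the error rates essentially unchanged. Simulation of the main rows (40,000 trials each, pooled t-test) agrees.

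**B. Failure itself causes the 3 extra points, and patients who fail do not otherwise differ.** Completers then differ by about 0 and the completer test keeps its 5% error. All randomised patients differ by (fB − fC) × 3: 0.30 points at 29% / 19% and 0.60 at 34% / 14%, to the disadvantage of Buzzy. The completer analysis does not show this.

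**C. Power of an all-randomised analysis, 50 per arm.** Assume equal failure rates f in both arms, failures scoring 3 points higher, and 3.10 as the SD within successes and within failures. The difference is 2(1 − f) plus 2f times the share of the effect that persists in failed attempts. The control variance is 3.10² + f(1 − f) × 3². In the Buzzy arm the 3 becomes 4 if half the effect persists and 5 if none does.

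Example, f = 24%, none persists: difference 0.76 × 2 = 1.52; SDs √(9.61 + 0.1824 × 9) = 3.35 and √(9.61 + 0.1824 × 25) = 3.76; SE = √[(3.35² + 3.76²)/50] = 0.713; power about 56%.

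| Failures | Full effect persists | Half | None | Completers only |
|---|---|---|---|---|
| 24% | 84% | 71% | 56% | 79% (38 per arm) |
| 10% | 87% | 82% | 76% | 86% (45 per arm) |

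Section XI.2 does not say whether 3.10 already includes failed attempts. If it does, the within-group SD is 2.82 at 24% failures and 2.97 at 10%. Power is then about 89% at either rate (full) and 62% or 79% (none), against 86% and 89% for completers.

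**The case against.** The strongest reply is that the size is speculative. No document gives a failure rate, an arm gap or an excess, or says that the device affects success. The marked inflation to 13% needs both a 20-point gap and a 3-point excess. With smaller inputs, such as 10% versus 5% and 2 points, the bias is 0.10 and the error rate barely moves. Even 0.60 is under a third of the 2-point target. Three of the rate pairs above also average 24%, which is the room for exclusions and not an expected rate. The calculations use normal scores, whereas a FACES score with mean 3.42 and SD 3.10 is bounded and probably skewed. All of this stands, and it limits what can be said about size.

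The second reply is that pain of one successful insertion is a legitimate question, stated in advance, and that repeat needling would blur the device effect. It is legitimate, and it can be kept as a supporting analysis. But the plan never states it as its question, and choosing it does not restore comparability if different patients fail in the two arms. Rating the first attempt, whatever its outcome, also deals with the repeat-needling worry.

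Third, keeping failures can cost power. That is true, and the loss can be large. It is largest if the device does nothing in failed attempts, which is part of the answer for all patients randomised.

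None of these replies removes the defect: a stated rule drops patients after allocation, and nothing planned would reveal or bound the effect of doing so.

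**Conclusion.** The concern holds, and it should be resolved before enrolment. The exclusion is explicit; that no all-randomised analysis is planned is inferred from the silence of XI.1 and the absence of a separate protocol. Direction and size cannot be determined from the documents. With arm gaps of 10 to 20 percentage points and 1 to 3 points of excess pain, the bias is 0.1 to 0.6 points in either direction and the type I error is 5% to 13%. It is zero if rates and excess pain are equal across arms. The sample size of 38 per arm is not in error. Timing matters because a patient's involvement ends with the form (VII.E.6) and there is no follow-up (VII.E.7), so a rating not taken then cannot be recovered.

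**What to change.** 1. **VII.E.6:** state that every randomised patient completes the post-insertion questions, and that the pain rating refers to the first needle attempt and is taken after it, whether or not it succeeds.
2. **XI.1:** make all randomised patients, in their assigned arm, the main comparison. Keep the set with first-attempt success, 22 gauge, a listed site and no adjunct as a named supporting analysis.
3. **XI.1:** report first-attempt success, and exclusion events by reason, for each arm.
4. **VII.E.6:** state that expected site, gauge and need for adjuncts are recorded before the envelope is opened, so that those exclusions precede allocation. Patients screened out there are never randomised, which is consistent with item 2.
5. **XI.2:** restate the power for the all-randomised analysis within the ceiling of 100. Say whether 3.10 includes failed attempts and what effect is assumed in them. If the result is below 80%, say so.

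**Cost.** The change is wording in three sections, and the enrolment ceiling stays. If the post-insertion questions already cover failed attempts, no new data are needed; otherwise the timing of one rating must be fixed, and the form, which is not in the documents, may need a line for the attempt outcome. The real price is power: up to about 25 percentage points (86% to 62%, at 24% failures with 3.10 including them) if the device has no effect in failed attempts, and none if the 2-point effect holds fully there.

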**VI.13** **Describe EACH of your subject populations**

- **Include description of any control group(s)**
- **Specify the Inclusion/Exclusion criteria for EACH group**
- **Studies under IRB-03 enrolling non veterans as part of the subject population must present a compelling argument to the IRB for the inclusion of non-Veterans (e.g., insufficient number of Veterans; survey of VA employees; study of active duty military; study involving Veterans' family members), and the research is relevant to the care of Veterans or active duty military personnel.**

The study will be preformed on patients undergoing intravenous sedation for dental surgery.

This study is intended to be equally inclusive of male and female patients. An inclusion criterion is to be between ages 18 and 40. There are no medical conditions which would preclude participation in the study.

The control group (50% of total subjects) will have an IV started in the standard fashion.

The experimental group (50% of total subjects) will have an IV started in the standard fashion with use of the Buzzy.

**VI.14** **Provide an estimate of the total number of subjects that would be eligible for inclusion in each of your study populations (include your control population if applicable)**

The majority of the patient population treated by Oral and Maxillofacial Surgery is adults. All adults aged 18 to 40 who are receiving intravenous sedation for their dental surgery will be eligible for inclusion in the study. There are approximately forty patients per week at the college of dentistry who meet these criteria.

**VI.15** **Describe how you will have access to each of your study populations in sufficient number to meet your recruitment goals.**

The Oral and Maxillofacial Surgery department does approximately 2000 IV sedations at the UI College of Dentistry and Dental Clinics each year.

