### VII.D. Project Description (D)

**VII.D.1** **Check all materials/methods that will be used in recruiting subjects (you will need to attach copies of all materials at the end of the application):**

- Brochures -
- Use of any information available to the researchers or their colleagues because this person is a patient OR use of any information considered to be Protected Health Information (PHI) OR review of patient/clinic records - This study will use subjects already planned for surgical removal of third molars with the use of intravenous sedation. The study will be explained (both verbally and with the written form) to the patients at the beginning of their surgical appointment. The patient will be given the opportunity to discuss participation with their escort (typically a family member or friend and always an adult) as needed.

**VII.D.2** **List the individual data elements you will need to access/use from the patient or clinic records to identify potential subjects for recruitment**  
Age and planned sedation

**VII.D.3** **Describe why you could not practically recruit subjects without access to and use of the information described above**  
These two pieces (age and planned sedation) of information are our two inclusion criteria

**VII.D.4** **Describe why you could not practically obtain authorization from potential subjects to review their patient or clinic records for recruitment purposes.**  
Age and whether the procedure are planned are two inclusion criteria which must be known in order to ask the patient to participate in the study

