**VII.D.15     Check all materials that will be used to obtain/document informed consent:**

- Consent Document

**VII.D.16     Are you requesting a waiver of documentation of consent (either no subject signature or no written document)?**  
No

**VII.D.19     Before the subject gives consent to participate are there any screening questions that you need to directly ask the potential subject to determine eligibility for the study?**  
No

**VII.D.25     After the subject agrees to participate (signs consent), are there any screening procedures, tests, or studies that need to be done to determine if the subject is eligible to continue participating?**  
No

**VII.D.27     Discuss how much time a potential subject will have to agree to consider participation and whether or not they will be able to discuss the study with family/friends before deciding on participation.**  
We will use subjects planned for third molar removal with IV sedation (previously informed of the IV process). The study will be explained (verbal and written) to the patient at the start of their visit. The patient will have the opportunity to discuss participation with their escort (always an adult family member/friend) as needed. They will need to decide within a few minutes if they wish to participate.

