### IX.2

**What are the potential benefits to society in terms of knowledge to be gained as a result of this project?**

Decreased anxiety and fear in seeking treatment with IV sedation. Help decrease needle phobias and/or pain related to IV insertion, vaccinations, etc. This could help other oral and maxillofacial surgery clinics, and other organizations, such as blood banks, in seeking adult participants.

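### Adjunct and catheter-gauge exclusions are applied with no pre-envelope check, so after an unblinded allocation the known arm can affect who is analysed

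*Combined protocol and SAP*

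**What the plan says.** **Entry rules.** VII.D.3 states: "These two pieces (age and planned sedation) of information are our two inclusion criteria". VI.13 gives the 18 to 40 age range and adds: "There are no medical conditions which would preclude participation in the study". VII.D.25 asks whether, after consent, "are there any screening procedures, tests, or studies that need to be done to determine if the subject is eligible to continue participating"; the answer is No. VII.D.19, on screening questions put to the patient before consent, is also answered No.

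**Allocation.** Under VII.E.2, "when an eligible and participating subject is identified, the top most envelope will be chosen and opened to assign the group". VII.E.6 places this after the pre-insertion questionnaire: "After this portion is complete, their group (experimental vs control) will be determined from opening a blinded envelope". The tourniquet, the device (if assigned) and the 22-gauge cannulation follow. VII.E.1.a says that no subjects are blinded.

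**Exclusions.** The case exclusions come at the end of the VII.E.6 sequence. One sentence covers failure at the first attempt, another catheter gauge and an unlisted site; it begins: "We will plan to exclude cases where the IV is not obtained on the first attempt, if a smaller or larger gauge IV catheter is". A separate sentence deals with adjuncts: "The case will be excluded if adjunctive steps are taken to obtain IV access (i.e. Oral sedation, nitrous oxide, heat packs").

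**Analysis.** XI.1 names tests and models. It defines no analysis set and no reporting of exclusions by arm. XI.2 raises enrolment from 76 to as many as 100, partly to cover exclusions.

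**The concern.** Eligibility is in effect defined twice. The entry sections admit anyone of the right age with planned sedation. The procedures section then removes some of those patients for reasons that appear nowhere among the entry criteria.

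The order matters because using an adjunct or changing gauge involves discretion. Once the envelope is open, the patient knows whether the device will be used, and so does the operator who places it. A patient assigned to the standard procedure might be more inclined to ask for help, or an operator more inclined to offer it; the reverse is also possible. In either case the decision takes the patient out of the comparison.

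If such patients differ from the rest in pain or anxiety, which are the outcomes in I.5, the analysed groups are no longer those that randomisation formed. VII.E.6 has the baseline questions answered before the arm is known in order to avoid bias, and exclusion after the reveal works against that aim.

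**Working it through.** **1. The plan's own sample size.** Inputs from XI.1 and XI.2: SD 3.10, difference 2, two-sided alpha 0.05, power 80%.

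n per arm = 2 × (1.960 + 0.842)² × 3.10² / 2² = 37.7, rounded up to 38, or 76 in total. This matches XI.2.

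**2. Cost of spent allocations.** The allowance is 1 − 76/100 = 24%. Starting from 50 per arm with equal loss, power by the normal approximation is:

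| Loss | Analysed per arm | Power |
|---|---|---|
| 10% | 45 | 86.4% |
| 20% | 40 | 82.3% |
| 24% | 38 | 80.3% |
| 30% | 35 | 77.0% |

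Power falls below target only if loss from all causes exceeds 24%. The documents give no loss rate.

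**3. When selection causes bias.** Suppose a fraction e of an arm is excluded and those excluded average h points above that arm's full mean. The retained mean then falls by h × e/(1 − e). Equal and equally selective exclusion (20% in each arm) shifts both arms alike and gives no bias. Unequal exclusion does not cancel.

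**4. Illustration A: more exclusion in the control arm.** Assumptions: exclusions fall on the most anxious patients, and the anxiety–pain correlation r is 0.3 to 0.5. Removing the top fraction p of a standard normal variable leaves a mean of −φ(z₁₋ₚ)/(1 − p):

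- p = 2%: −0.049; p = 5%: −0.109; p = 10%: −0.195; p = 20%: −0.350.

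Shift in the pain difference = gap between the two means × r × 3.10:

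- 10% control, 2% device: gap 0.146, shift 0.14 to 0.23 points.
- 20% control, 5% device: gap 0.241, shift 0.22 to 0.37 points.

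The control mean is pulled down, so a true device benefit is understated.

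**5. Illustration B: more exclusion in the device arm.** Assumptions: 10% of controls and 20% of device patients are excluded, and there is no true effect. Bias = h × (0.20/0.80 − 0.10/0.90) = 0.139h:

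- h = 1: 0.14 points; h = 2: 0.28; h = 3: 0.42.
- Two-sided false-positive rates (45 and 40 analysed): about 5.5%, 7% and 9.5%.

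Here the device looks better than it is. Together, A and B span about 0.1 to 0.4 points, or up to roughly a fifth of the 2-point target (0.42/2 = 21%). More extreme inputs give more: 10% against 30% gives 0.32 to 0.95 points over the same values of h. Nothing in the documents helps to choose among these inputs.

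**The case against.** The strongest reply is about timing. VII.E.6 does not say when these exclusions are applied, and VII.E.2 opens the envelope only for a patient already judged eligible. Staff might therefore turn away a patient who has already had an adjunct. That is possible, but no listed criterion tells them to, and the wording of the exclusions describes events during the attempt at access. What stands is that the post-envelope timing is inferred from the sequence of procedures; it is not stated.

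A second reply is that a need fixed before the envelope cannot be caused by the arm. If the rule is applied consistently, such cases use up places without creating a systematic imbalance. This is correct, and XI.2 budgets for lost places. It confines the bias argument to decisions made after the envelope.

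Third, heat packs and gauge changes may reflect veins more than anxiety, and illustration A assumes perfect selection on anxiety. That also stands, and it is one reason to treat the figures as illustrations only.

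Two stronger readings are tempting. A reader might infer that the need for an adjunct or another gauge is often known when the patient arrives; the documents give neither frequency nor timing. A reader might also set the exclusions against IX.2 ("Help decrease needle phobias and/or pain related to IV insertion, vaccinations, etc") and call that statement unsupportable. IX.2 answers a form question about possible benefit to society and is not a planned efficacy claim, so it needs no change on this account.

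**Conclusion.** The concern holds as a gap in design and analysis. The adjunct and gauge exclusions have no counterpart at entry and, in the order of procedures, operate mainly after an open allocation, so the plan as written lets the known arm affect membership of the analysed groups.

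The documents do not fix the direction or the size of the resulting bias. A reader might conclude that the effect must be understated because anxious controls would leave, but the opposite pattern is equally open. The range of about 0.1 to 0.4 points rests wholly on assumed exclusion rates, correlations and score gaps; only the SD of 3.10 and the 2-point target come from the plan. Loss of power is secondary up to 24% total loss.

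Failed first attempts and changes of site are also excluded after allocation. They are outside this point, and the fix below does not deal with them.

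**What to change.** 1. Add two items to the study form, completed after consent and before the envelope is opened: whether an adjunct has already been given or is planned, and whether a 22-gauge catheter is intended. A patient with an adjunct given or planned, or with another gauge intended, is not randomised.
2. List these as exclusion criteria in VI.13 and align the answer to VII.D.25. VII.D.19 can stay as it is, because it concerns questions put directly to the patient before consent.
3. In VII.E.6, replace the exclusion for adjunct use or gauge changes decided after the envelope. These patients complete the post-insertion questions, the change is recorded, and they are analysed in their assigned arm.
4. In XI.1, state this rule, report such cases by arm, and give the analysis without them as a sensitivity analysis.

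None of this restricts what the surgeon may do; it changes only when eligibility is settled and who is analysed. The cost is two form items and a short amendment. The retained cases will slightly dilute the contrast, by an amount that cannot be worked out from the documents, and the sensitivity analysis will show how much they matter. The required analysed number stays at 38 per arm.
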